## Subject Request for Withdrawal from Study

If a parent would like to withdraw their infant from the study, the Withdraw from Study form will be given to the parent/s to complete and the infant will be removed from the study.

## Criteria for Cessation of Enrollment Pending DSMB Review of Safety Data

1. Two or more infants experience an SAE related to iNO treatment
2. Two or more infants are discontinued from the study due to safety concerns

## Data Collection and Follow-up for Withdrawn Subjects

Subjects who are withdrawn from the study will not be included in the final analysis. All AEs and SAEs will continue to be collected on withdrawn subjects throughout hospitalization, and that data will be reviewed by the DSMB when necessary.

---

Current Version 9/10/2020 IRBNet #: 1170748  
Date:

Previous Version Page 18 of 25  
Date:

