## Study Outcome Measures (Endpoints)

- Maternal demographics (listed under the data collection section of the protocol)
- Infant measures (listed under the data collection section of the protocol)

Current Version Date:	9/10/2020	IRBNet #: 1170748
Previous Version Date:		Page 14 of 25

- Incidence of death or BPD measured at 36 weeks post menstrual age (yes or no)
  - BPD will be defined as need for supplemental oxygen for at least 28 days. Severity of BPD will be determined at 36 weeks postmenstrual age. Infants with no need for supplemental oxygen will be classified as mild BPD. Continued requirement for supplemental oxygen (<0.3 FiO2) will be considered moderate BPD. Infants requiring >0.3 FiO2 and or positive pressure respiratory support will be diagnosed with severe BPD. The need for continuing oxygen therapy will be determined by a room air challenge. We will prospectively collect data that will allow us to define BPD as recommended by the 2018 NICHD report
- Pulmonary arterial pressure based on serial echocardiograms)
- Oxygen saturation level (average for each 24-hour period after enrollment)
- Arterial pressure and oxygen saturation will be measured up to 2-weeks or until the treatment is discontinued, whichever is shorter.

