## Statistical Analysis Plan

### Primary Objective Analysis

Data will be analyzed to define the demographic and clinical characteristics of the two study cohorts (iNO and placebo) and the infants without early PH (not enrolled for treatment, please see Fig. 1). Chi square test for categorical variables and student's t test or non-parametric equivalent test for continuous variables will be used. Relative Risk (with 95% CI) for death or BPD will be calculated for the placebo and iNO treatment groups. The outcomes of infants without early PH will also be compared with the two study cohorts (iNO and placebo). Logistic regression will be performed to adjust for significant covariates if needed (unlikely because of randomization and stratification). Similarly, treatment and placebo groups will be compared to determine the short-term benefits of iNO treatment for PH in preterm infants.

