### Mitigation of Risks:

We will measure levels of methemoglobin with blood gases as is current standard of care in the NICU. The first methemoglobin level will be checked within 4-8 hours of treatment initiation, and then repeated every 24-48 hours during the intervention. Methemoglobinemia can be reversed by stopping the iNO.

Our device has an alarm set at 0.7ppm for live monitoring of NO2 that is set well below the threshold for any adverse effect.

Study team will seek clearance from the clinical team before performing echocardiogram to ensure the safety of the infant. If an infant is clinically unstable, study echocardiogram can be delayed or cancelled

During the course of study, the attending clinicians may request unmasking of intervention (iNO or placebo) only if oxygenation index is higher than 40 for at least 4 hours or if there is risk of

---

Current Version 9/10/2020 IRBNet #: 1170748  
Date:

Previous Version Page 17 of 25  
Date:

death due to hypoxic respiratory failure without starting iNO. If the infant is on iNO, treatment will continue. If the infant is on placebo, iNO treatment may be allowed. The PI will be notified immediately. A protocol violation will be filed and intention to treat principle will apply.

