## Early Withdrawal of Subjects

### Investigator Withdrawal of Subjects

- A. The following stopping criteria will be followed: Patient experiences a serious adverse event (defined per regulation) related to study drug
- B. Patient experiences any one of the following:
  - I. Pulmonary edema due to worsening of left ventricular dysfunction
  - II. Elevated met Hb level (>5%) on 2 samples 6 hours apart or > 7.5% on a single reading
  - III. If nitrogen di-oxide (NO2) concentration is more than 3 ppm for 6 hours or more than 5 ppm on a single reading
- C. Investigator judgement

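### Withdrawn infants are left out of the final analysis, so the primary relative risk is not a comparison of all randomised infants

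*Combined protocol and SAP*

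**What the plan says.** The section Data Collection and Follow-up for Withdrawn Subjects states: "Subjects who are withdrawn from the study will not be included in the final analysis". Adverse events and serious adverse events are still recorded after withdrawal until the hospital stay ends. Nothing is said about the BPD assessment.

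The routes to withdrawal are these:

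- **Drug-related event** (Investigator Withdrawal of Subjects): "Patient experiences a serious adverse event (defined per regulation) related to study drug".
- **Toxicity** (same section): pulmonary edema from worsening left ventricular function, an NO2 limit, or "Elevated met Hb level (>5%) on 2 samples 6 hours apart or > 7.5% on a single reading".
- **Investigator's discretion** (same section), with no limits given.
- **Parent request** (Subject Request for Withdrawal from Study): "the Withdraw from Study form will be given to the parent/s to complete and the infant will be removed from the study".

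Primary Objective Analysis gives the estimand only as "Relative Risk (with 95% CI) for death or BPD will be calculated for the placebo and iNO treatment groups" and names no analysis population. Secondary Objective Analysis names none either. Intention to treat appears once, under Mitigation of Risks, for infants whose assignment is unmasked at the clinician's request: "A protocol violation will be filed and intention to treat principle will apply".

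**The concern.** The drug-related and toxicity grounds can arise only once study gas has started, so after randomisation. The other two can arise then. Removing these infants makes membership of the primary comparison depend on what happened under treatment. The methemoglobin and NO2 triggers should fall mainly on the iNO arm. If the infants removed from that arm do worse than those who stay, the relative risk is biased in favour of iNO.

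Two features make this harder to repair later:

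- **The outcome may be lost.** Death is on the adverse-event list and would still be recorded, but BPD is not on that list. Study Outcome Measures says "The need for continuing oxygen therapy will be determined by a room air challenge", and Data Collection also ties BPD status to that test. If it is not done at 36 weeks, the infant cannot be put back into the analysis.
- **The scope is unclear.** The list under Investigator Withdrawal of Subjects is introduced as stopping criteria but sits under a withdrawal heading. A reader cannot tell whether an infant who meets one stops study gas or leaves the study, and with it the analysis.

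The conflict with the intention-to-treat sentence is direct only for an infant who is both unmasked and withdrawn. Elsewhere the analysis set is simply undefined.

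**Working it through.** **Inputs from the documents.** 34 infants per arm; death or BPD 80% on placebo; a 30% relative decrease, so 0.80 × 0.70 = 56% on iNO; alpha 0.05, taken as two-sided because sidedness is not stated. No withdrawal allowance is given.

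**The plan's own figure.** For 80% vs 56% with 80% power, the pooled two-sided formula is n = [1.96√(2·0.68·0.32) + 0.842√(0.80·0.20 + 0.56·0.44)]² / 0.24², which gives 59 per arm. The stated 34 is not reproduced. That is a separate problem, and the present point does not depend on it.

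**Assumptions.** k infants are withdrawn, all from iNO, with outcome risk q. The documents fix neither k nor q.

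**Step 1: shift in the relative risk.** With p the true iNO risk, RR after exclusion = [(34p − kq)/(34 − k)] / 0.80. For example, p = 0.56, q = 1, k = 3 gives (19.04 − 3)/31 = 0.517, and 0.517/0.80 = 0.65.

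| True RR | q | k=1 | k=2 | k=3 | k=5 |
|---|---|---|---|---|---|
| 0.70 | 1.0 | 0.68 | 0.67 | 0.65 | 0.61 |
| 0.70 | 0.9 | 0.69 | 0.67 | 0.66 | 0.63 |
| 1.00 | 1.0 | 0.99 | 0.98 | 0.98 | 0.96 |
| 1.00 | 0.9 | 1.00 | 0.99 | 0.99 | 0.98 |

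If q = p, the RR does not move.

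**Step 2: false-positive chance.** All pairs of binomial counts were enumerated (80% in both arms, q = 1, uncorrected chi-square, result favouring iNO). The chance is 2.6% with none removed and 3.2%, 3.3%, 3.9% and 5.1% for k = 1, 2, 3 and 5.

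**Step 3: a single data set.** Chi-square = N(ad − bc)²/(product of the four margins). The RR interval is exp[ln RR ± 1.96√(1/a − 1/n₁ + 1/c − 1/n₂)], where a and c are the numbers with the outcome on iNO and placebo, and n₁ and n₂ the arm sizes.

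| iNO vs placebo | Chi-square | p | RR (95% CI) |
|---|---|---|---|
| 20/34 vs 27/34 (all randomised) | 3.38 | 0.066 | 0.74 (0.533–1.030) |
| 18/32 vs 27/34 (two dropped) | 4.08 | 0.043 | 0.71 (0.499–1.005) |
| 17/31 vs 27/34 (three dropped) | 4.48 | 0.034 | 0.69 (0.481–0.992) |

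Dropping two carries the chi-square test past 0.05 but not the RR interval past 1. Dropping three carries both.

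**Step 4: the opposite direction.** Drop two placebo infants with the outcome instead. Then 19/34 vs 27/34 (p = 0.038, RR 0.70, 0.50–0.99) becomes 19/34 vs 25/32. By the same formulas p = 0.055 and RR = 0.72 (0.50–1.02), so a significant result is lost.

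**Step 5: power.** Exact chi-square power for 80% vs 56% is 59% at 34 vs 34, 55% at 31 vs 34, and 53% at 31 vs 31.

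**The case against.** The strongest reply is that few infants will be affected and the direction of bias is not fixed.

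- **Toxicity withdrawals should be rare.** Raised methemoglobin and NO2 are described as seen above 20 ppm, and treatment starts at 20 ppm. Infants with myocardial dysfunction on the first echocardiogram are excluded, and the pulmonary edema event is described as arising in infants with pre-existing left ventricular dysfunction. Enrolment also pauses if "Two or more infants are discontinued from the study due to safety concerns".
- **Ordinary stopping of gas is not withdrawal.** Under Study Visits, non-responders and infants whose hypertension resolves are weaned without being called withdrawn. The ambiguity is confined to the investigator-withdrawal list. If that list means only stopping gas, exclusions shrink mainly to parent requests, where the outcome may be unobtainable anyway.
- **The example in Step 3 is a borderline case.** With two iNO infants with the outcome removed, the exact chance that a non-significant chi-square turns significant in favour of iNO is 0.7% with no effect and 7.6% at the planned rates. Fisher's exact test stays above 0.05 after dropping two (0.064) or three (0.062).

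These points stand, and they limit the likely size of the bias. They do not make the rule sound. The investigator's discretion is open-ended and untouched by the toxicity arguments. Parent-request withdrawals are dropped on either reading, even where the parents would allow the outcome to be used. The chi-square test in Step 3 is the one the plan names for categorical variables.

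**Conclusion.** The concern holds. Followed as written, the plan removes randomised infants from the primary comparison because of later events, and nothing in the analysis sections overrides this. The shift in the relative risk is modest for small numbers: about 0.03 to 0.05 at the planned effect, and about 0.02 with no effect, for two or three withdrawn iNO infants who all have the outcome. It is zero if withdrawn infants carry their arm's risk, and it favours placebo if the poor-outcome withdrawals are on placebo. These sizes rest on assumed withdrawal counts; three to five toxicity withdrawals are less likely than one or two. The correction is needed because the rule undermines the randomised comparison, 34 per arm leaves little margin, and an uncollected 36-week outcome cannot be recovered. Safety reporting is not affected, since adverse events are kept.

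**What to change.** Replace the exclusion sentence with a rule along these lines:

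> All randomised infants are included in the primary analysis in the arm assigned, whether or not study gas was stopped, the assignment was unmasked, open-label iNO was given or the infant was withdrawn, unless the parents refuse further use of data.

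In addition:

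1. State the same analysis set in Primary Objective Analysis.
2. State that the 36-week death or BPD assessment, including the room air challenge, is still obtained for infants who stop study gas or are withdrawn, unless parents refuse.
3. Report refusals by arm, with best-case and worst-case bounds on the relative risk.
4. Keep the analysis without withdrawn infants only as a labelled sensitivity analysis.
5. Reconcile Mitigation of Risks, Investigator Withdrawal of Subjects, Subject Request for Withdrawal from Study, and Data Collection and Follow-up for Withdrawn Subjects, so that stopping study gas and leaving the study are separate events. The clinical stopping thresholds stay as they are.

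The cost is short edits to these sections plus collection of an outcome already planned for the other infants. Some parents may refuse, so some outcomes may still be missing; the bounds in item 3 show how much that matters.

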### Study Site(s)/Location(s) and Number of Subjects

This is a single site clinical study to be conducted at the Neonatal Intensive Care Unit of AdventHealth for Children. A total of 136 infants will be enrolled in the trial, and 68 of those infants will be randomized (34 in each arm). Screen failures, which are defined as infants who were consented but the echocardiogram showed no PH, will be enrolled into the comparison group and no further intervention will occur for them. To compare the incidence of death or BPD, outcome data will continue to be collected on the comparison group for the duration of their hospital stay.

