## Adverse Event Reporting

An adverse event is defined as “any untoward medical occurrence associated with the use of a drug in humans, whether or not considered drug related.”

A serious adverse event is defined as an adverse event “if, in the view of the investigator, it results in any of the following outcomes: Death, a life-threatening adverse event, inpatient hospitalization or prolongation of existing hospitalization, a persistent or significant incapacity or substantial disruption of the ability to conduct normal life functions, or a congenital anomaly/birth defect. Important medical events that may not result in death, be life-threatening, or require hospitalization may be considered serious when, based upon appropriate medical judgment, they may jeopardize the patient or subject and may require medical or surgical intervention to prevent one of the outcomes listed in this definition. Examples of such medical events include allergic bronchospasm requiring intensive treatment in an emergency room or at home, blood dyscrasias or convulsions that do not result in inpatient hospitalization, or the development of drug dependency or drug abuse.”

Adverse events that meet criteria for reporting will be submitted to the FDA and/or IRB as applicable. Given this high-risk patient population, a number of adverse events are expected. The key monitoring function will be to assess whether evidence is accruing that suggests a differential adverse event rate associated with treatment. AE's collected include elevated met hemoglobin or nitrogen dioxide, rebound pulmonary hypertension after discontinuing iNO, myocardial dysfunction/heart failure, hypotension, pulmonary hemorrhage, pneumothorax, PDA (if treated), NEC (stage 2b or 3), culture proven sepsis (treated with antibiotics  $\geq$  5 days), IVH (grade III or IV), ROP (severe), death, cardiac arrest or other life-threatening events. These adverse events will be collected from the time the subject starts intervention or placebo through the end of study participation (at 36 weeks corrected gestational age) and will be documented in the subject's chart.

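### Withdrawn infants are left out of the final analysis, and the safety stops listed as withdrawal can take randomised infants out of the primary comparison

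*Combined protocol and SAP*

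**What the plan says.** All references are to the combined protocol and SAP.

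- **Data Collection and Follow-up for Withdrawn Subjects** sets the analysis rule without qualification: "Subjects who are withdrawn from the study will not be included in the final analysis". On data it adds: "All AEs and SAEs will continue to be collected on withdrawn subjects throughout hospitalization".
- **Investigator Withdrawal of Subjects** opens its list with "The following stopping criteria will be followed: Patient experiences a serious adverse event (defined per regulation) related to study drug". It continues with pulmonary edema from worsening left ventricular function, a methemoglobin threshold ("Elevated met Hb level (>5%) on 2 samples 6 hours apart or > 7.5% on a single reading"), an NO2 threshold and, as item C, the investigator's judgement with no criteria attached. The next section removes infants at a parent's request.
- **Criteria for Cessation of Enrollment** pauses enrolment when two or more infants leave the study for safety reasons.
- **Mitigation of Risks** has the only intention-to-treat statement, for infants unmasked by the clinical team: "A protocol violation will be filed and intention to treat principle will apply".
- **Primary Objective Analysis** says "Relative Risk (with 95% CI) for death or BPD will be calculated for the placebo and iNO treatment groups". It names no analysis set.
- **Adverse Event Reporting** lists events to collect, including "IVH (grade III or IV), ROP (severe), death, cardiac arrest or other life-threatening events". BPD is not in the list.
- **Study Site(s)/Location(s) and Number of Subjects** says of the unrandomised infants that "outcome data will continue to be collected on the comparison group for the duration of their hospital stay".

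**The concern.** Randomisation makes the two arms comparable only if infants stay in the analysis whatever happens afterwards. Here the exclusion rule and the list of safety stops appear under the same withdrawal heading, so an infant whose gas is stopped for toxicity appears to leave the primary comparison as well. The methemoglobin and NO2 triggers belong essentially to iNO. A drug-related SAE, investigator judgement and parental withdrawal can occur in either arm. If the excluded infants differ in outcome from those who remain, the relative risk for death or BPD no longer compares the groups that were randomised.

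Follow-up is the second issue. Death would still be recorded as an adverse event, but no text requires BPD status at 36 weeks for a withdrawn infant. That could limit a later analysis of all randomised infants.

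**Working it through.** **1. Which rule governs an infant stopped for toxicity?**

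- For study withdrawal: the heading over the list, and the enrolment-pause rule, which describes safety stops as leaving the study.
- For stopping gas only: the list calls its items stopping criteria. Study Visits weans non-responders off gas without calling them withdrawn, and continues serial echocardiograms to 14 days of life however long treatment lasts. The severity grading speaks of discontinuing the intervention for grade 2 events.
- Nothing in the withdrawal sections themselves chooses the second reading, and the analysis section names no set that would override the exclusion rule. Followed as written, the exclusion applies.

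**2. The plan's own figure.** Sample Size Determination gives 34 per arm for 80% falling by a relative 30% (to 0.80 × 0.70 = 56%), with 80% power and alpha 0.05. The two-sided pooled formula, with mean proportion 0.68, is

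n = [1.960 √(2 × 0.68 × 0.32) + 0.842 √(0.80 × 0.20 + 0.56 × 0.44)]² / 0.24² = 58.1, so 59 per arm.

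The 34 is not reproduced; 34 per arm gives about 57% power. That is a separate matter. What counts here is that 34 per arm is also the number to be randomised per arm, so nothing is set aside for exclusions.

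**3. What one or two exclusions do.** The documents give no withdrawal rate, so one and two are assumed counts. They were chosen because enrolment pauses at two safety discontinuations; that does not cap the total. Starting counts are the nearest whole numbers to the planned rates: placebo 0.80 × 34 = 27.2, taken as 27; iNO 0.56 × 34 = 19.04, taken as 19. A second start, with 20 iNO events, represents a result just short of significance. The test is Pearson chi-square without continuity correction. The relative risk (RR) interval is exp[ln RR ± 1.96 √(1/a − 1/n + 1/b − 1/m)], with a/n for iNO and b/m = 27/34.

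| iNO infants removed | iNO rate | RR (95% CI) | p |
|---|---|---|---|
| None, from 19/34 | 55.9% | 0.704 (0.499–0.993) | 0.038 |
| One with the outcome: 18/33 | 54.5% | 0.687 (0.481–0.980) | 0.030 |
| One without: 19/33 | 57.6% | 0.725 (0.516–1.018) | 0.054 |
| Two with: 17/32 | 53.1% | 0.669 (0.463–0.966) | 0.024 |
| Two without: 19/32 | 59.4% | 0.748 (0.535–1.044) | 0.077 |
| None, from 20/34 | 58.8% | 0.741 (0.533–1.030) | 0.066 |
| One with: 19/33 | 57.6% | 0.725 (0.516–1.018) | 0.054 |
| Two with: 18/32 | 56.3% | 0.708 (0.499–1.005) | 0.044 |

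From 19/34, the iNO rate moves by −1.3 or +1.7 points for one infant and −2.8 or +3.5 points for two. Against the planned 23.5-point difference (27/34 − 19/34) that is 6–7% and 12–15%. In the last row the chi-square p-value passes 0.05 while the RR interval still just includes 1, so that crossing depends on which of the two is read.

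**4. With no true effect.** Exact enumeration of two Binomial(34, 0.80) arms gives the chance of p < 0.05 favouring iNO:

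- none removed: 2.6%
- one or two iNO infants with the outcome removed: 3.2% and 3.3%
- one or two iNO infants without it removed: 1.7% and 0.9%

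If removal is unrelated to outcome, only sample size is lost.

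**The case against.** The strongest reply is that the list is about treatment. The protocol elsewhere separates stopping gas from leaving the study, and its one intention-to-treat statement shows the principle intended. This stands in part: the status of toxicity stops is ambiguous. It does not remove the concern, because the unqualified exclusion is the only rule covering withdrawal and no text in those sections limits it.

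The second reply is that the triggers will seldom be met. The protocol associates methemoglobinemia and raised NO2 with doses above 20 ppm, whereas treatment starts at 20 ppm and is weaned down. The NO2 alarm is set at 0.7 ppm against triggers of 3 and 5 ppm, and infants with myocardial dysfunction are excluded. This stands. Investigator judgement, however, has no stated limit.

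The third reply is that outcome data will exist anyway. Oxygen and ventilation data come from the chart in a single NICU, and the adverse event list is not worded as exhaustive. This also stands for much of the BPD definition. A reader might infer that BPD status would be lost for good; the documents do not support that. The part at risk is the room air challenge at 36 weeks, which no text requires after withdrawal. Nor does the provision for comparison infants show that withdrawn randomised infants go unfollowed.

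A reader might also take the drug-related SAE criterion to mean that infants who die are dropped from a death-or-BPD endpoint. The SAE definition does include death, but treating a death as a withdrawal is a strained reading.

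**Conclusion.** The exclusion rule is wrong as written: it allows randomised infants to leave the primary comparison for post-randomisation reasons, some tied to active treatment. The conclusion rests on reading the stopping criteria as study withdrawal, which the heading and the enrolment-pause rule favour but do not settle.

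The numbers involved should be small. The removal counts above are assumptions, and the effect on the false-positive chance in those cases is modest. At 34 per arm, though, one or two exclusions are enough to change a borderline conclusion in either direction.

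A reader might infer that the rule biases the trial towards iNO. The documents do not support that. They give no rate for these events and nothing links a methemoglobin or NO2 reading to death or BPD; removing infants without the outcome works against iNO. The size and direction of any bias are unknown. The change should be made because it is cheap and the 36-week assessment has to be arranged in advance.

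**What to change.** 1. In Primary Objective Analysis and in the section on withdrawn subjects, state that all randomised infants are analysed in their assigned arm unless parents withdraw permission to use the data. This replaces the exclusion sentence.
2. In Investigator Withdrawal of Subjects and the section on withdrawn subjects, state that stopping study gas is not withdrawal from the study, and that these infants are followed to 36 weeks postmenstrual age for death and BPD, including the room air challenge, as well as for adverse events.
3. In the enrolment-pause criteria, reword item 2 to count infants whose study gas is stopped for safety concerns, so that the pause still works after change 2.

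The cost is a protocol amendment, plus a room air challenge and chart data at 36 weeks for the few infants concerned. Outcome data are already collected through the hospital stay for unrandomised infants, so the added work is small.

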### Potential Risks:

A potential risk associated with iNO is methemoglobinemia. This risk is minimal as we are using low concentrations of iNO. Occasionally an extremely preterm infant is unstable and performing echocardiogram could cause oxygen desaturation and a temporary increase in FiO2 requirement. Heart failure has been described as a potential risk for iNO treatment. However, this complication is noted only among the patients with ischemic heart disease or myocardial dysfunction. No severe side effects of iNO have been reported at the starting dose of 20 ppm. We will not include any infants with myocardial dysfunction noted on the initial echocardiogram. We will start weaning iNO treatment if worsening of hemodynamic status is noted on serial echocardiograms based upon the recommendations of our cardiologists. Very rarely, nitric oxide can chemically react with oxygen to make nitrogen dioxide (NO2) that can cause inflammation of the airways if the level exceeds beyond 5 parts per million.

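### In DSMB/DSMC review, how long adverse events are counted depends on whether an infant was withdrawn; the effect is probably small, and one common window would remove it

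*Combined protocol and SAP*

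**What the plan says.** *Adverse Event Reporting* lists the adverse events to be collected. It starts collection when the infant starts iNO or placebo and runs it "through the end of study participation (at 36 weeks corrected gestational age". The same section sets the purpose: "The key monitoring function will be to assess whether evidence is accruing that suggests a differential adverse event rate associated with treatment".

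*Data Collection and Follow-up for Withdrawn Subjects* sets a different end: "All AEs and SAEs will continue to be collected on withdrawn subjects throughout hospitalization". It adds that "that data will be reviewed by the DSMB when necessary". The sentence before these reads: "Subjects who are withdrawn from the study will not be included in the final analysis".

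*Investigator Withdrawal of Subjects* gives the triggers. One is "Patient experiences a serious adverse event (defined per regulation) related to study drug". The others are pulmonary edema from worsening left ventricular function, methemoglobin limits, nitrogen dioxide limits and investigator judgement. A parent may also withdraw the infant. *Data and Safety Monitoring Board (DSMB) or Equivalent* schedules a safety review at half of enrollment by a committee it calls the DSMC; I take DSMB and DSMC to be the same body.

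**The concern.** Two end points for adverse event collection apply within one randomised population, and which one applies is decided by something that happens after randomisation. The scope differs too: a listed set of events for retained infants, all events for withdrawn ones.

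The protocol's central safety question is whether event rates differ between arms. A late event such as sepsis, severe ROP or death after 36 weeks would count as an adverse event for a withdrawn infant, but not for an otherwise similar infant who stayed in. If withdrawals are unevenly split between arms, part of any difference the committee sees would come from the collection rule. Some imbalance toward iNO is plausible: the protocol says nitrogen dioxide forms in mixtures of iNO and oxygen, and that methemoglobin depends on nitric oxide dose and time.

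**Working it through.** The documents give no figure for adverse event observation time, withdrawal rate or length of stay, so there is no stated figure to reproduce. The check is the size of the mismatch at arm level.

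**Inputs from the protocol.** Gestation at birth is 23+0 to 29+6 weeks (*Inclusion Criteria*, Step 1). Randomisation is at 48–96 hours, so I take gas start as day 2–4. Collection ends at 36 weeks (*Adverse Event Reporting*). There are 34 infants per arm (*Study Site(s)/Location(s) and Number of Subjects*).

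**Assumptions not in the protocol.** Hospital stay runs 0–56 days past 36 weeks; all withdrawals are on iNO; their later events are pooled with everyone else's. The last two make the result an upper bound for each count.

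**Scheduled window for a retained infant.**
- Born at 23+0: 36+0 minus 23+0 = 91 days; less 2–4 days = 87–89 days.
- Born at 29+6: 36+0 minus 29+6 = 43 days; less 2–4 days = 39–41 days.
- Range 39–89 days; midpoint (39 + 89)/2 = 64 days.

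**Increase in the iNO arm's mean window** = withdrawn infants × extra days / 34, also shown as a percentage of 64 days:

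| Withdrawn on iNO | 14 extra days | 28 extra days | 56 extra days |
|---|---|---|---|
| 1 | 0.41 d (0.6%) | 0.82 d (1.3%) | 1.65 d (2.6%) |
| 2 | 0.82 d (1.3%) | 1.65 d (2.6%) | 3.29 d (5.1%) |
| 5 | 2.06 d (3.2%) | 4.12 d (6.4%) | 8.24 d (12.9%) |

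With zero extra days every cell is zero. If every infant had the shortest window, two withdrawals at 56 days would give 3.29/39 = 8.4%. Two is a natural count to look at because *Criteria for Cessation of Enrollment* pauses the trial once two infants are discontinued for safety.

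**At the scheduled review.** If half of enrollment means about 17 randomised infants per arm (an assumption), two withdrawals at 56 days give 2 × 56/17 = 6.6 days, or 6.6/64 = 10.3%. That is a ceiling, since some of those infants would not yet have reached 36 weeks. One late event counted only because its infant was withdrawn would move that arm's rate by 1/17 = 5.9 points.

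**Effect of the exclusion, as an illustration.** Suppose two of 34 iNO infants meet a toxicity trigger and are withdrawn. The true proportion is 2/34 = 5.9%. With withdrawn infants left out it is 0/32 = 0%.

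**The case against.** The strongest reply is that the mismatch touches few infants in a limited setting. Withdrawn infants are outside the final analysis, the statistical analysis plan names no between-arm adverse event comparison, and their data reach the committee only as needed. The protocol also expects little toxicity: it associates methemoglobin and nitrogen dioxide events with doses above 20 ppm, the trial starts at 20 ppm, and it calls the methemoglobinemia risk minimal. Several triggers (a drug-related serious event as judged under masking, investigator judgement, parental request) can arise in either arm. All of this stands, and it is why the point is minor. It does not remove the point, because the committee's review is where the protocol places its differential-rate question.

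A reader might infer something stronger: that the final comparison is biased against iNO. The documents do not support that. The longer follow-up never enters the final analysis, an iNO excess of withdrawals is an inference, and the exclusion works toward hiding iNO harm. A hospital stay ending before 36 weeks would even shorten a withdrawn infant's window.

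A reader might also take the per-infant increase, up to 56/88 = 64% at 23+0 weeks or 56/40 = 140% at 29+6 weeks, as the size of the problem. Those figures describe one withdrawn infant, not an arm.

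Nor does it follow that late harm in retained infants goes unrecorded. *Data Collection* lists death, NEC, ROP, IVH and culture-proven infection with no 36-week limit. It does not list pneumothorax, pulmonary hemorrhage or cardiac arrest, and nothing says later entries are graded or assessed for causality as adverse events. Ending collection at 36 weeks, the time of the primary outcome, is a legitimate choice; extending it to discharge for everyone would be a preference.

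**Conclusion.** The two sections give different end points and must be reconciled. In committee review the observation window depends on withdrawal, which may be somewhat more frequent on iNO through the methemoglobin and nitrogen dioxide limits. For two iNO withdrawals the shift is at most about 3 days, or 5% of mean observation time, in a full arm. This rests on an assumed stay of up to 56 days past 36 weeks, a 64-day midpoint window and full pooling. The shift could be zero, and its direction is not established.

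The same passage raises a related problem. Leaving withdrawn infants out of the final analysis can remove the very events that led to withdrawal. It also sits badly with *Mitigation of Risks*, which invokes intention to treat for infants whose treatment is unmasked. Severity: minor.

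**What to change.** Reconcile *Adverse Event Reporting* with *Data Collection and Follow-up for Withdrawn Subjects*. State that every between-arm adverse event comparison, including the DSMC review, uses one window, gas start to 36 weeks corrected gestational age, for all randomised infants. Keep withdrawn infants in that comparison in their randomised arm. List any events after 36 weeks separately, marked as outside the common window.

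Optionally, record adverse events during and shortly after a research screening echocardiogram. *Potential Risks* warns that "performing echocardiogram could cause oxygen desaturation", yet collection opens only at gas start. This would not apply to all 136 enrolled infants, because *Subject Recruitment and Screening* uses a clinically ordered echocardiogram in place of the study one when available.

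The cost is protocol wording and slightly more tabulation. With a common window the scheduled difference in observation time is zero days.
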